**The first 3 subjects:**

- The first 3 patients in the safety lead-in will be enrolled in a **staggered fashion**, with at least 2 weeks from time of completion of RT to first dose of study drugs for the subsequent patient.
- For the first 3 subjects, the **maximal tumor diameter may not exceed 5 cm**.
- After the 3rd subject is enrolled, **enrollment will halt and subjects will be observed for 40 days for DLTs (see DLT definitions below)** and to assess overall safety. At the end of the DLT period for the first 3 subjects, the safety data will be reviewed by the Sponsor and the NYU DSMC. If 1 or less of the first 3 subjects experiences a DLT during the DLT observation period, the maximal tumor diameter for subsequent subjects may be increased to **6.6 cm**. If  $\geq 2$  of the first 3 subjects experiences a DLT during the DLT observation period, the study will halt and the sponsor, NYU DSMC, and the FDA, may redesign the dosing and schedule of the study treatment or will stop the study for unacceptable toxicity.
- Continuation of enrollment will occur once all of the first 3 subjects have completed the Day 40 safety assessments and the final safety review decisions have been made.

After the first 6 subjects are enrolled, enrollment will stop and subjects will be observed for 40 days for **DLTs**. After all subjects in the Safety Lead-In cohort have completed the DLT observation period, the safety data will be reviewed by the Sponsor and the NYU DSMC. Continuation of enrollment will occur once all of the subjects have completed the Day 40 safety assessments and the final safety review decisions, including whether the study should be discontinued or proceed to phase II, have been made.

If  $\geq 2$  of the first 6 subjects experiences a DLT during the 40 day DLT observation period, the sponsor, and the FDA, may redesign the dosing and schedule of the study treatment or will stop the study for unacceptable toxicity.

If  $\geq 2$  of the first 6 subjects are unable to complete RT due to toxicity related to the planned treatment, the study will be stopped and the overall safety will be re-assessed by the sponsor and DSMC.

If 1 or less of the first 6 subjects experiences a DLT at the end of the 40 day DLT observation period, the study will continue enrollment onto the phase II part of the study.

DLT will be determined by toxicities related to nivolumab, ipilimumab, or RT during or beginning over the first 40 days of treatment as defined below. Subjects who experience DLT will be discontinued from study therapy and will enter the post-study follow-up phase of the study. Adverse events that meet DLT criteria but occur outside the DLT window will be classified as unacceptable AEs and study treatment will be discontinued.

Subjects are evaluable for DLTs if they have received at least one dose of nivolumab and ipilimumab, have completed RT per protocol, and have completed safety assessments over the entire DLT evaluation period (days 1 through 40). Any subject who discontinues treatment or withdraws from the study prior to completing the DLT evaluation period for any reason other than the occurrence of a protocol-defined DLT or other AE leading to study treatment discontinuation will be replaced. Each replacement patient will be assigned a unique patient number. Any patient who discontinues after the DLT observation period will not be replaced.

CONFIDENTIAL

This material is the property of the NYU School of Medicine. Do not disclose or use except as authorized in writing by the study sponsor

Subjects who do not experience a DLT during the DLT period (40 days) and remain on study after the DLT period will continue nivolumab and ipilimumab administration for up to 2 years or until the subject discontinues study therapy as per protocol. All subjects who discontinue study therapy will enter the post-study follow-up phase of the study.

#### 6.1.1.1 **Definition of Dose-Limiting Toxicity (DLT) for the Safety Lead-In**

The DLT period for the Safety Lead-In is considered the first 40 days of study therapy, and will include labs and other evaluations taken at C1D40 (end of the first 40 days). The frequency, time to onset, and severity of toxicities, as well as the success of standard medical management and dosing interruptions/ delays, will be analyzed to determine if a given toxicity should be considered a DLT for dose decision purposes. The final decision of whether or not the AE meets the DLT definition will be based on a careful review of all relevant data by the Sponsor and the NYU DSMC. The treating investigator may also be consulted.

A DLT is defined as any non-hematologic grade  $\geq 3$  adverse event (AE) that is at least possibly, probably or definitely related to nivolumab or ipilimumab or RT during the DLT period with the exceptions noted below.

The following will be classified as DLT:

- Any Grade 2 drug-related uveitis or eye pain or blurred vision that does not respond to topical therapy and does not improve to Grade 1 severity within 7 days OR requires systemic treatment.
- Any Grade  $\geq 2$  drug-related pneumonitis or interstitial lung disease that does not resolve to Grade 1 within 7 days and systemic steroids (also see Pulmonary Adverse Event Management Algorithm in Appendix 4).
- Any Grade 3 drug-related bronchospasm, hypersensitivity reaction, or infusion reaction, regardless of duration.
- Any Grade 3 non-hematologic, drug-related adverse event, with the following criteria:
  - Grade 3 drug-related uveitis, pneumonitis, diarrhea, or colitis of any duration will be classified as DLT.
  - Grade  $\leq 3$  symptoms attributable to brain/intracranial edema that downgrades to Grade  $\leq 2$  within 7 days, or to Grade  $\leq 1$  or baseline within 14 days after onset will not be classified as DLT (for **rules for managing brain/intracranial edema**, see Section 6.2.5 below).
  - Any  $\geq$  grade 2 neurological AE lasting  $> 7$  days will be considered a DLT.
- Grade  $\geq 3$  thrombocytopenia ( $< 50,000 \text{ mm}^3$ ), which will be classified as DLT
- Grade  $\geq 3$  neutropenia ( $\text{ANC} < 1000 \text{ mm}^3$ ), which will be classified as DLT
- Any drug-related liver function test (LFT) abnormality that meets the following criteria will be classified as DLT (also see Hepatic Adverse Event Management Algorithm):
  - AST or ALT ( $> 5 \times \text{ULN}$ ) for  $> 2$  weeks
  - AST or ALT ( $> 8 \times \text{ULN}$ )
  - Total bilirubin ( $> 5 \times \text{ULN}$ )
  - Concurrent AST or ALT ( $> 3 \times \text{ULN}$ ) and total bilirubin ( $> 2 \times \text{ULN}$ )
- Grade  $\geq 3$  lymphopenia will not be classified as DLT as this is frequently observed at baseline in newly diagnosed GBM patients.

CONFIDENTIAL

This material is the property of the NYU School of Medicine. Do not disclose or use except as authorized in writing by the study sponsor

- Isolated grade  $\geq 3$  electrolyte abnormalities that are asymptomatic, considered unrelated or unlikely related to study treatment, and are reversed within 48 hours with replacement will not be considered DLT. However, recurrence of the same grade  $\geq 3$  electrolyte abnormality during the DLT period will be considered a DLT.

While rules for adjudicating DLTs are specified above, an AE of Grade  $<3$  (except if listed as exempt above), may also be defined as a DLT after a consultation with the overall study Principal Investigator, based on the safety profile of nivolumab and/or ipilimumab. In the absence of clinical abnormality, repeat laboratory testing will be conducted to confirm significant laboratory findings prior to designation as a DLT.

For guidance on assessing the relationship of AEs to nivolumab and ipilimumab, RT, or study procedures, see Appendix 5. The sponsor may request information to justify the causality assessment of DLTs, as needed.

**Note:** See Section 8.1, Adverse Event Definitions, for **expected AEs** related to nivolumab or ipilimumab.

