#### **6.4.3 Cycle 1, Day 15 (C1D15) and Day 29 (C1D29) and all subsequent mid-cycle visits (i.e., Day 15 and 29 visits)**

The subject will have the Safety Procedures detailed below performed prior to initiating study treatment. Required assessments and study drug administration windows include  $\pm 3$  days of scheduled visit.

- Adverse event assessment
- Concomitant medication collection
- Symptom-directed physical exam as clinically indicated by the investigator or qualified designee at all mid-cycle visits
  - For cycle 1, day 15 (C1D15) visit only, a complete physical exam and neurological exam must be performed. For all other mid-cycle visits, only a symptom-directed physical exam is necessary.
- Vital signs: When scheduled at the same visit as other procedures, vital signs should be measured prior to clinical laboratory assessments or research blood sample collection.
  - Weight (can be taken within 3 days of scheduled study drug administration)
  - Vital signs on all treatment days subsequent to C1D1 will be assessed and documented prior to the infusions and then approximately 30 minutes after the completion of the infusions:
    - Temperature, resting blood pressure, pulse and respiration rate.
- Serum chemistry: sodium, potassium, chloride, bicarbonate, calcium, magnesium, phosphorous, glucose, albumin, creatinine, blood urea nitrogen (BUN), uric acid, ALT, AST, total bilirubin, direct and/or indirect bilirubin, alkaline phosphatase (ALP), lactate dehydrogenase (LDH), amylase, and lipase.
- Hematology: WBC count, 3-cell differential (ANC, monocyte count, lymphocyte count), hemoglobin, hematocrit, and platelet count
- Urinalysis: glucose, blood, pH, specific gravity, ketones, and urine protein

**Study Drug:** Nivolumab only will be administered in an outpatient setting as an IV infusion at the specified doses (for details see Administration of Study Drugs, Section 5.3). The doses of study drug must be adjusted each cycle for changes in body weight of  $\geq 10\%$ . The weight used for dosing can be taken within 3 days of scheduled study drug administration.

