#### **6.4.4 Cycle 2, Day 1 (C2D1) and all subsequent Day 1 cycle visits (i.e., C3D1, C4D1)**

The subject will have the C2D1 Safety Procedures detailed below performed prior to initiating study treatment. Required assessments and nivolumab administration windows include  $\pm 3$  days of scheduled

CONFIDENTIAL

This material is the property of the NYU School of Medicine. Do not disclose or use except as authorized in writing by the study sponsor

visit. For administrative purposes, ipilimumab administration can be  $\pm$ 5 days of the scheduled administration day.

- Adverse event assessment
- Concomitant medication collection
- Complete physical exam, including neurological exam, and KPS assessment
- Vital signs: When scheduled at the same visit as other procedures, vital signs should be measured prior to clinical laboratory assessments or research blood sample collection.
  - Weight (can be taken within 3 days of ipilimumab administration)
  - Vital signs will be assessed and documented prior to the infusion and then approximately 30 minutes after the completion of the infusion:
    - Temperature, resting blood pressure, pulse and respiration rate.
- Serum chemistry: sodium, potassium, chloride, bicarbonate, calcium, magnesium, phosphorous, glucose, albumin, creatinine, blood urea nitrogen (BUN), uric acid, ALT, AST, total bilirubin, direct and/or indirect bilirubin, alkaline phosphatase (ALP), lactate dehydrogenase (LDH), amylase, and lipase.
- Hematology: WBC count, 3-cell differential (ANC, monocyte count, lymphocyte count), hemoglobin, hematocrit, and platelet count
- T cell subsets (CD3, CD4, and CD8 counts) at C2D1, C4D1, C6D1, and C8D1 only.
- Urinalysis: glucose, blood, pH, specific gravity, ketones, and urine protein
- Thyroid stimulating hormone (TSH), free T4
- Pregnancy test (urine or serum  $\beta$ -HCG) for women of child-bearing potential
- Research Blood Samples (C2D1 only, not required at subsequent visits): Note: Research blood samples will be taken at only 2 timepoints: **baseline** and **C2D1** (end of week 6). All subjects will have the below research blood samples collected.
  - NYUSoM subjects: A total of 40 mL (four 10 mL purple top EDTA tubes) of whole blood will be drawn and immediately sent to the below sites:
    - One (1) 10 mL tube will be sent to the CBRD at NYUSoM for acquisition of whole blood, buffy coat, and plasma samples.

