## 15.1 Appendix 1: Schedule of Events for Main Study Cohort

STUDY DAY ►		Day -21 to -1 	C1 D1 	C1 D8 	C1 D15 and D29	C2 D1	Week 8+ 	End of Rx 	30-Day Post-Drug 	90-Day Post-Drug 	Surv F/u 
Study Team Procedures											
Informed Consent 		X									
Demographics		X									
Inclusion/Exclusion Criteria 		X									
Medical/Disease History 		X									
MGMT testing 		X									
KPS Assessment 		X	X			X		X	X	X	
Concomitant Medications 		X	X		X	X		X	X	X	
Height and Weight 		X	X		X	X		X	X	X	
Vital Signs 		X	X	X	X	X		X	X	X	
Complete Physical Exam 		X	X		X 	X		X			
Directed Physical Exam 				X	X 				X	X	
Adverse Events 		X	X	X	X	X		X	X	X	
Survival								X	X	X	X
Laboratory/Cardiology Assessments											
Serum Chemistry 		X	X		X	X		X	X	X 	
Hematology 		X	X		X	X		X	X	X 	
T cells (CD3, CD4, CD8) 		X				X 					
Urinalysis 		X			X	X		X			
Coagulation 		X									
Hepatitis B and C 		X									
Pregnancy Test 		X	X			X		X	X	X	
TSH, free T4 		X	X			X		X 	X	X 	
12-Lead ECG 		X									
Study Treatment											
Radiotherapy: 3 Gy x 15 fractions (45 Gy total) 				X							
Nivolumab IV 			X		X	X					
Ipilimumab IV 			X			X					
Imaging Assessments											
MRI Brain 		X					X 				
Chest X-ray 		X									
Research Procedures											
Archival tumor tissue 		X									
Research blood samples 			X			X					
Research MRI (sodium MRI) 		X					X 				
Surgical tumor specimen 		X 									
Tumor biopsy (optional) 								X			

CONFIDENTIAL

This material is the property of the NYU School of Medicine. Do not disclose or use except as authorized in writing by the study sponsor

One treatment cycle will be defined as 42 days

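### The 40-day DLT window is meant to close on Day 40 labs, but no visit list or schedule contains a Day 40 assessment

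*Combined protocol and SAP*

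**What the plan says.** **What the lead-in decision requires.** Section 6.1.1.1 sets the DLT period at 40 days and says that it "will include labs and other evaluations taken at C1D40 (end of the first 40 days". For the first three subjects, Section 6.1.1 states: "Continuation of enrollment will occur once all of the first 3 subjects have completed the Day 40 safety assessments". It says the same for all six, and Section 8.5 repeats it. Section 6.1.1 counts a subject as evaluable only if, among other conditions, they "have completed safety assessments over the entire DLT evaluation period (days 1 through 40". Section 7.3.1 replaces subjects who are not fully evaluable.

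**What happens outside the window.** Section 6.1.1 adds: "Adverse events that meet DLT criteria but occur outside the DLT window will be classified as unacceptable AEs".

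**What is scheduled.** Section 6.4.1 lists labs on C1D1. Section 6.4.3 covers "Cycle 1, Day 15 (C1D15) and Day 29 (C1D29) and all subsequent mid-cycle visits". Section 6.4.4 covers C2D1. Appendix 1 has the same columns and no Day 40 column. It also states: "One treatment cycle will be defined as 42 days".

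**What the window length is.** The protocol gives three lengths:
- 28 days: in the decision rules of the synopsis, and in one decision rule of Section 3.1.2.
- 40 days: in the synopsis and Sections 3.1.2, 6.1, 6.1.1, 6.1.1.1, 7.3.1 and 8.5.
- 53 days: at the start of Section 6.1.1, tied there to four weeks after the last radiation fraction.

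**The concern.** A site that follows the Schedule of Events exactly will not collect the laboratory data on which the go/no-go decision is said to rest. Several DLT definitions in Section 6.1.1.1 are purely laboratory (platelets, neutrophils, liver tests), and such events can occur without symptoms. An abnormality that begins on Day 33, say, and is first seen on Day 43 could be dated to Day 43. It would then be an unacceptable AE, not a DLT, and would not count toward 2 of 3 or 2 of 6.

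The timing matters. At five fractions a week from Day 8, radiotherapy ends at about Days 26 to 28, so the uncovered stretch is the period just after it. The Day 29 labs are drawn before that day's nivolumab dose, so nominally no in-window lab follows the third dose.

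It is also unclear whether a subject whose last in-window labs were on Day 29 counts as evaluable or should be replaced.

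**Working it through.** **Step 1: calendar.** The cycle is 42 days (Section 6.4.1, Appendix 1), so C2D1 = 42 + 1 = Day 43. Nominal lab days are 1, 15, 29 and 43. The stated closing point, labs on Day 40, cannot be reproduced from the schedule.

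**Step 2: nominal gap.** The last in-window labs are on Day 29, and 40 − 29 = 11 days (Days 30 to 40), or 11/40 = 27.5% of the window.

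**Step 3: effect of visit windows.** Section 6.4.3 ("Required assessments and study drug administration windows include") and Section 6.4.4 ("Required assessments and nivolumab administration windows include") each allow 3 days either side. Appendix 1, footnotes 17 and 18, allows samples up to 3 days before a visit.
- C1D29 labs can fall on Days 26 to 32, and C2D1 labs on Days 40 to 46.
- If C2D1 labs are drawn on Day 40, the gap is 0 days.
- If C2D1 labs are drawn after Day 40, the gap is 40 − 32 = 8 days with Day 29 labs drawn late, and 40 − 26 = 14 days with them drawn early.

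**Step 4: the other stated windows.**

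| Window | Nominal labs inside | Nominal days after last lab |
|---|---|---|
| 28 days | 1, 15 | 28 − 15 = 13 |
| 40 days | 1, 15, 29 | 40 − 29 = 11 |
| 53 days | 1, 15, 29, 43 | 53 − 43 = 10 |

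None of the three ends on a nominal lab day. For 28 days the C1D29 allowance (from Day 26) reaches the end of the window. For 40 days the C2D1 allowance (from Day 40) just reaches it. For 53 days the next visit, C2D15, is Day 42 + 15 = 57, earliest Day 54, which does not.

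**Step 5: illustrative effect on the 2-of-6 rule.** The documents give no DLT rate and no share of DLTs that only a lab test would show, so both are assumptions. Take a true rate p per subject, onset uniform over 40 days, a share s of DLTs detectable only by lab, and no counting of those in the last 11 days. The counted rate is p′ = p × (1 − s × 11/40), and P(2 or more of 6) = 1 − (1 − p′)^6 − 6p′(1 − p′)^5.

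For p = 0.30: s = 0.25 gives p′ = 0.279, s = 0.5 gives 0.259, and s = 1 gives 0.2175.

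| True rate p | All counted | s = 0.25 | s = 0.5 | s = 1 |
|---|---|---|---|---|
| 0.20 | 0.345 | 0.311 | 0.277 | 0.212 |
| 0.30 | 0.580 | 0.534 | 0.487 | 0.388 |
| 0.40 | 0.767 | 0.722 | 0.671 | 0.558 |

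**The case against.** A reader might infer that laboratory DLTs in the last 11 days are bound to be lost, and that the lead-in really observes only 29 days. The documents do not support that, for these reasons:
- Sections 6.1.1 and 6.1.1.1 themselves require Day 40 labs and assessments, and enrollment may not resume without them. The defect is a required assessment left out of the schedule.
- The C2D1 window and the pre-visit sampling rule both reach Day 40, so the draw is already permitted.
- Section 6.1.1 counts toxicities that begin within the 40 days, and Section 6.1.1.1 has the sponsor and the DSMC adjudicate using time to onset. No text equates onset with first detection.
- Under the 53-day definition, Day 43 labs are inside the window.
- Section 6.2.3 calls for laboratory or other clinical evaluation at least weekly when an AE delays dosing.
- An out-of-window event still stops that subject's treatment. Related grade 3 or 4 toxicity still enters the Bayesian rule of Section 3.5.1, which covers all 24 subjects, including the first six.

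All of this stands, and it turns a certainty into a possibility. It does not remove the gap. Day 40 is only the earliest edge of Days 40 to 46, and nothing requires it. A dosing delay interrupts the cycle count (Section 6.2.3), so C2D1 can move later. Weekly evaluation starts only once an AE has been recognized, and adjudication cannot supply a value that was never measured. The 53-day definition contradicts the other sections and does not cure the problem. The later Bayesian monitoring does not repair the lead-in decision.

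**Conclusion.** The inconsistency holds whatever is assumed about toxicity rates: the text requires Day 40 labs for enrollment decisions and evaluability, and no schedule lists them. The stretch without a required draw is nominally 11 days and ranges from 0 to 14 days under the visit windows, before any dosing delay. Laboratory DLTs in that stretch may be missed or dated outside the window. Any resulting undercount makes the 2-of-3 and 2-of-6 rules less likely to trigger.

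The size is not known. At an assumed 30% rate the loss in P(2 or more of 6) runs from about 5 percentage points (0.580 to 0.534) to 19 (0.580 to 0.388). The larger figure is a worst case and should not be read as the expected effect: it takes every DLT to be laboratory-only, while many DLT categories in Section 6.1.1.1 are clinical. Even the smaller figure assumes uniform onset, no draw during Days 30 to 40, and exclusion of every late laboratory finding.

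**What to change.** 1. Reconcile the 28-, 40- and 53-day statements (synopsis; Sections 3.1.2, 6.1, 6.1.1, 6.1.1.1, 7.3.1 and 8.5) to one DLT window. Which length applies is for the sponsor and the DSMC to decide.
2. List the matching end-of-window safety assessment in Section 6.4 and Appendix 1, tied to calendar days from first dose. It should not be tied to the cycle count, which pauses when dosing is delayed.
3. Where the C2D1 visit window already allows it, as it does at Day 40, let the pre-dose C2D1 labs serve as that assessment, so that no extra visit is needed. If the 53-day window is kept, no existing visit window reaches its last day, and a further draw would have to be listed.
4. State how an abnormality first found at that assessment is dated for the DLT count, and use the same wording in Sections 6.1.1, 7.3.1 and 8.5.

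The cost is mostly wording. The small downside is less flexibility in the timing of that draw, or a lead-in review that starts a few days later.

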### 6.1.2 Main Study Cohort

Following completion of the Safety Lead-In, subjects meeting eligibility criteria will be enrolled onto the phase II portion of the study (Main Study Cohort). The Phase II trial is a one-stage design phase II trial with analyses for safety (see Section 7 for Statistical Methods). A total of 24 patients are anticipated to be treated in the Main Study Cohort.

After all screening, registration and baseline procedures have been completed as detailed on the **Schedule of Events (Appendix 1)**, subjects will begin study treatment. If the initial doses of nivolumab and ipilimumab are found to be safe, subjects in the phase II portion of the study will be treated as below:

On C1D1, subjects will be administered one dose of nivolumab 3 mg/kg IV and one dose of ipilimumab 1 mg/kg IV.

On C1D8, subjects will be administered RT to a total dose of 45 Gy, given in 15 fractions of 3 Gy on consecutive days (i.e., 5 days per week).

On C1D15, subjects will receive nivolumab 3 mg/kg. Thereafter, nivolumab 3 mg/kg IV will continue once every 2 weeks.

On C1D29, subjects will receive ipilimumab 1 mg/kg IV. Thereafter, ipilimumab 1 mg/kg IV will continue once every 6 weeks.

Nivolumab and ipilimumab administration will continue for up to 2 years or until disease progression, death, intolerable toxicity, or the subject discontinues study therapy as per any of the protocol subject withdrawal guidelines. Subjects who are discontinued from study therapy will enter the post-study follow-up phase of the study.

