### Main Study Cohort

### Surgical Study Cohort

### 3.1.2 General Study Design

This is an open label, phase II trial of nivolumab, ipilimumab and hypofractionated radiation therapy in adult patients with newly diagnosed, *MGMT* unmethylated GBM with the primary objective of determining the overall survival at 1 year.

**Safety Lead In:** The study will start with a Safety Lead-In consisting of the first 6 subjects (Section 6.1.1), which will be conducted to further define the safety and tolerability of nivolumab and ipilimumab when given in combination with hypofractionated radiotherapy in previously untreated, newly diagnosed GBM patients with unmethylated *MGMT* promoter. Note, special safety provisions are included for the first 3 subjects enrolled (see Section 6.1.1). After the first 6 subjects are enrolled, enrollment will stop and subjects will be observed for 40 days for dose-limiting toxicities (DLTs, see DLT definitions is Section 6.1.1.1). After all subjects in the Safety Lead-In cohort have completed the DLT observation period, the safety data will be reviewed by the Sponsor and the NYU DSMC. If 2 or more of the first 6 subjects in the Safety Lead-in experiences a DLT during the 40 day DLT observation period, the sponsor and the FDA, may redesign the dosing and schedule of the study treatment or will stop the study for unacceptable toxicity. If 1 or less of the first 6 subjects experiences a DLT at the end of the 28 day DLT observation period, the study will continue enrollment onto the phase II part of the study.

**Main Study Cohort:** The Phase II trial is an open-label, single-stage study at the nivolumab and ipilimumab doses and schedules determined to be safe in combination with RT in the Safety Lead-in.

The phase II trial will enroll a total of 24 subjects, including those from the safety lead-in. Monitoring of toxicity attributable to study treatment will be continually assessed during the phase II trial using a

CONFIDENTIAL

This material is the property of the NYU School of Medicine. Do not disclose or use except as authorized in writing by the study sponsor

Bayesian monitoring approach, assessing safety with the accrual of every three additional patients (see Primary Safety Endpoints, Section 3.5).

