#### **Safety Lead-In/Main Study Cohort:**

On C1D8, seven days after nivolumab and ipilimumab administration, all subjects will be administered radiotherapy (RT) to a total dose of 45 Gy, given in 15 consecutive fractions of 3 Gy each fraction.

On C1D15, subjects will receive nivolumab 3 mg/kg IV. Thereafter, nivolumab administration will continue once every 2 weeks.

On C2D1, subjects will receive ipilimumab 1 mg/kg IV. Thereafter, ipilimumab administration will continue once every 6 weeks.

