There will be no dose escalations or reductions allowed.

Subjects may be dosed with nivolumab no less than 18 days from the previous dose. Subjects may be dose with ipilimumab no less than 37 days from the previous dose.

Doses of nivolumab and/or ipilimumab may be interrupted, delayed, or discontinued depending on how well the subject tolerates the treatment. Dosing visits are not skipped, only delayed. See Section 6.2 for dose delay and discontinuation criteria.

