- The Surgical Study Cohort will open once the Safety Lead-In is completed. Patients in the **Surgical Study Cohort** will undergo craniotomy and tumor re-resection within 2 weeks from the first dose of nivolumab and ipilimumab. Patients will begin HFRT 3 weeks after surgery.

All subjects will receive HFRT to a total dose of 45 Gy, given in 15 consecutive fractions of 3 Gy each fraction.

All subjects will continue to receive nivolumab 3 mg/kg IV every 2 weeks and ipilimumab 1 mg/kg every 6 weeks from day of first nivolumab and ipilimumab administration.

One treatment cycle will be defined as 42 days (6 weeks), corresponding to 3 doses of nivolumab and one dose of ipilimumab.

Nivolumab and ipilimumab administration will continue for all subjects for 2 years or until disease progression, intolerable toxicity, death, or the subject meets another withdrawal criteria as per the Subject Withdrawal guidelines (Section 6.12), whichever comes first. Subjects who are discontinued from study therapy will enter the post-study follow-up phase of the study as per Section 6.10.

All subjects will be evaluated every 8 weeks with radiographic imaging to assess response to treatment. Disease assessments will be made using standard RANO criteria. However, non-traditional iRANO criteria (Appendix 3) may be considered for patient management. Adverse events will be monitored throughout the trial and graded in severity according to the guidelines outlined in the NCI-CTCAE version 4.03.

The investigator shall take responsibility for and shall take all steps to maintain appropriate records and ensure appropriate supply, storage, handling, distribution and usage of trial treatments in accordance with the protocol and any applicable laws and regulations.

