### 6.1.1 **Safety Lead-In**

The first 6 subjects enrolled onto the study will be evaluated as a Safety Lead-In cohort. After all screening, registration and baseline procedures are completed as detailed on the Schedule of Events (Appendix 1), subjects will begin the study regimen.

On Day 1 of Cycle 1, subjects will be administered one dose of nivolumab 3 mg/kg IV and one dose of ipilimumab 1 mg/kg IV.

On Day 8 of Cycle 1, subjects will be administered RT to a total dose of 45 Gy, given in 15 fractions of 3 Gy.

CONFIDENTIAL

This material is the property of the NYU School of Medicine. Do not disclose or use except as authorized in writing by the study sponsor

On Day 15 of Cycle 1, nivolumab 3 mg/kg IV will be administered, and subsequently continue once every 2 weeks.

Ipilimumab 1 mg/kg IV will continue once every 6 weeks after the first ipilimumab dose on Cycle 1 Day 1.

The **DLT evaluation period** will be defined as the **first 53 days** on study. The DLT period will start with the first infusion (**Day 1**) and will **end 4 weeks following the final day of radiation**, ie, **Days 1-53**.

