    - Three (3) 10 mL tubes will be sent to the IMC at NYUSoM and immediately processed for isolation of PBMCs.

**Study Drugs:** Nivolumab and ipilimumab will be administered in an outpatient setting as an IV infusion at the specified doses defined in the Safety Lead-In or the phase II trial (for details see Administration of Study Drugs, Section 5.3). The doses of study drug must be adjusted each cycle for changes in body weight of  $\geq$ 10%. The weight used for dosing can be taken within 3 days of study drug administration.

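### Section 6.1.2 schedules the second Main Study Cohort ipilimumab dose 28 days after the first, against a 37-day minimum and the C2D1, six-weekly schedule given elsewhere

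*Combined protocol and SAP*

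**What the plan says.** Section 6.1.2 describes treatment of subjects enrolled after the Safety Lead-In. Both drugs are given on C1D1, radiotherapy starts on C1D8, and nivolumab continues from C1D15 every two weeks. Then: "On C1D29, subjects will receive ipilimumab 1 mg/kg IV", followed by ipilimumab every six weeks.

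The other text that governs this cohort gives a different date:

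- Section 3.1.3 (Safety Lead-In/Main Study Cohort): "On C2D1, subjects will receive ipilimumab 1 mg/kg IV".
- Section 6.1.1 (Safety Lead-In): "Ipilimumab 1 mg/kg IV will continue once every 6 weeks after the first ipilimumab dose on Cycle 1 Day 1".
- Section 6.1: "One treatment cycle will be defined as 42 days (6 weeks), corresponding to 3 doses of nivolumab and one dose of ipilimumab".
- Section 6.4.3, which covers C1D15, C1D29 and later mid-cycle visits: "Nivolumab only will be administered in an outpatient setting as an IV infusion".
- Section 6.4.4, which covers C2D1 and later Day 1 visits: "Nivolumab and ipilimumab will be administered in an outpatient setting as an IV infusion at the specified doses defined in the Safety Lead-In".
- Appendix 1: the grid marks ipilimumab at C1D1 and C2D1 and leaves the D15/D29 column empty. Note 26 repeats the six-week interval.

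Two rules limit how closely ipilimumab doses may be spaced. Section 5.3.1 states: "Subjects may be dose with ipilimumab no less than 37 days from the previous dose". Section 6.2.3.2 separately bars resuming ipilimumab sooner than six weeks, plus or minus 5 days, after the previous dose.

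**The concern.** A dosing section that disagrees with the visit procedures leaves staff unable to comply with both. Anyone who follows 6.1.2 breaks 5.3.1 and 6.4.3; anyone who follows 6.4.3 and 6.4.4 departs from 6.1.2.

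The six-week interval was chosen for safety. Section 1.2.3 reports that the earlier lung cancer regimens, which gave ipilimumab every three weeks, led 39% of subjects to stop for treatment-related events, and adopts the less frequent schedule for that reason. A first interval of 28 days lies nearer to the rejected 21 days than to the chosen 42.

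Section 3.1.2 also commits phase II to the "nivolumab and ipilimumab doses and schedules determined to be safe in combination with RT in the Safety Lead-in". The Lead-In schedule in 6.1.1 has no ipilimumab on Day 29, so 6.1.2 read literally would give later subjects a schedule that the Lead-In did not test. Section 7.3.2 would then combine the two groups in one primary analysis. If the 6 Lead-In subjects count toward the 24, up to 24 − 6 = 18 subjects could be affected.

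**Working it through.** This is day counting; no power or sample-size formula is involved.

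**Inputs**

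| Quantity | Value | Source |
|---|---|---|
| First ipilimumab dose | C1D1 = Day 1 | 6.1.2 |
| Second dose as written | C1D29 = Day 29 | 6.1.2 |
| Second dose elsewhere | C2D1 = Day 42 + 1 = 43 | 3.1.3, 6.4.4, Appendix 1 |
| Planned interval | 6 weeks ± 5 days | 5.2.1, 5.3.1 |
| Minimum interval | 37 days | 5.3.1 |
| Cycle | 42 days, one ipilimumab dose | 6.1, 6.4.1 |
| Maximum duration | 96 weeks, 16 cycles | 5.2.1 |

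**1. The plan's own minimum.** 6 × 7 − 5 = 37 days. This reproduces the figure in 5.3.1, and it also follows from 6.2.3.2.

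**2. Interval under 6.1.2.** 29 − 1 = 28 days; 37 − 28 = 9 days short. If the dose is given 5 days late, on Day 34, the interval is 34 − 1 = 33 days; 37 − 33 = 4 days short. No date inside the window complies.

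**3. Interval under C2D1.** 43 − 1 = 42 days, or 37 to 47 days with the window. Every date in the window complies.

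**4. Doses per cycle.** Days 1 and 29 both fall in Cycle 1, which gives two ipilimumab doses in a cycle defined as containing one.

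**5. Later doses.** Under 6.1.2 the days are 1, 29, 71, 113, ..., 659, where 659 = 29 + 15 × 42. In visit terms these are C1D1, then C1D29, C2D29, C3D29, ..., C16D29. Every dose after the first lands on a visit that 6.4.3 lists as nivolumab only. Over 96 × 7 = 672 days that is 17 doses. Under C2D1 the days are 1, 43, 85, 127, ..., 631, where 631 = 1 + 15 × 42. That is 16 doses, one for each of the 16 cycles.

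**6. Early exposure.** Cumulative ipilimumab doses:

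| By study day | 6.1.2 | C2D1 |
|---|---|---|
| 28 | 1 | 1 |
| 40 | 2 | 1 |
| 53 | 2 | 2 |

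These are the three lengths that the protocol gives in different places for the dose-limiting toxicity window. The counts differ at only one of them.

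**7. Is there support for C1D29 anywhere else?** None was found for this cohort. Section 5.2.1 gives two rather than three nivolumab doses per cycle, but still one ipilimumab dose per 42 days. The Surgical Study Cohort's second ipilimumab dose on C1D15 follows a first dose on C1D-29. That is a separate schedule and does not explain the entry in 6.1.2.

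**The case against.** The strongest reply is that this is one wrong visit label with an obvious reading. The text that staff use visit by visit is right: 6.4.3 names C1D29 and gives nivolumab only, 6.4.4 gives both drugs at C2D1, and the Appendix 1 grid agrees. The 37-day rule is a further barrier. Nothing in the documents shows that anyone was dosed on C1D29. All of this stands. It makes harm less likely, but it does not make 6.1.2 correct.

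Three narrower points:

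- The dose-limiting toxicity windows apply only to the Safety Lead-In, whose own section has the right schedule. The counts in step 6 therefore affect no toxicity decision for subjects treated under 6.1.2. This is correct; they describe early exposure and nothing more.
- Seventeen doses against 16 requires the full 96 weeks. Section 3.1.3 expects about 10 months of participation and cites a median PFS of 6 months on standard therapy. By Day 182 both schedules give 5 doses, and by Day 300 both give 8. This is also correct. The main effect is the short first interval, with each later dose 14 days early.
- The sentence beside the 37-day rule sets an 18-day nivolumab minimum, which two-weekly dosing cannot meet. That is a defect in 5.3.1, but the ipilimumab figure does not depend on it: it equals 42 − 5 and agrees with 6.2.3.2.

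**Conclusion.** Section 6.1.2 is wrong as written. It sets a first ipilimumab interval of 28 days where the protocol intends 42 and permits no fewer than 37, a shortfall of 9 days, or 4 at the late edge of the window. It also conflicts with the cycle definition, the visit procedures and the Schedule of Events. Correction should be mandatory because this is an operative instruction for a study drug in the section that governs phase II treatment.

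The conclusion rests on counting C1D1 as Day 1 and on 42-day cycles, both stated in the protocol. Any effect on patients depends on 6.1.2 having been followed in preference to 6.4.3, 6.4.4 and Appendix 1, which the documents cannot show. Type I error, power and sample size are unaffected.

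**What to change.** In Section 6.1.2, change C1D29 to C2D1 for the second ipilimumab dose and leave the six-weekly continuation as it is. The section then agrees with 3.1.3, 6.1.1, 6.4.3, 6.4.4 and Appendix 1.

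Check the dosing records to confirm that no Main Study Cohort subject received ipilimumab on C1D29, and record any who did as a protocol deviation.

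The cost is a one-line protocol correction and a check of records for at most 24 subjects at a single site. Design, sample size and analysis do not change.
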